## 5.2 Duration of Therapy

Duration of therapy will depend on individual response and toxicity. In the absence of disease progression or unacceptable toxicity, treatment will continue for 4 to 6 total cycles of brentuximab/AD, depending on treatment response or until one of the following criteria applies:

- Disease progression
- Intercurrent illness that prevents further administration of treatment
- Unacceptable adverse event(s), including Grade 4 neuropathy or other Grade 4 events felt to be related to brentuximab
- Any toxicity requiring dose delays of greater than 2 weeks
- Participant demonstrates an inability or unwillingness to comply with the regimen and/or documentation requirements
- Participant decides to withdraw from the study
- General or specific changes in the participant's condition render the participant unacceptable for further treatment in the opinion of the treating investigator

## 5.3 Criteria for Removal from Study Treatment

Participants will be removed from study treatment when intercurrent illness, toxicity, inability to participate or a change in condition occurs. The reason for treatment removal and the date the participant was removed must be documented in the study-specific case report form (CRF). Alternative care options will be discussed with the participant.

In the event of unusual or life-threatening complications, participating investigators must immediately notify the Principal Investigator/Sponsor, [name] at [contact].

## 5.4 Duration of Follow Up

All participants will be followed for next line of therapy and overall survival. Additionally, participants who have been removed from study treatment for unacceptable adverse events will be followed until resolution or stabilization of the adverse event.

## 5.5 Criteria for Removal from Study

Participants will be removed from the study upon death or withdrawal of consent. The reason for study removal and the date the participant was removed must be documented in the study-specific case report form (CRF).

## 6. EXPECTED TOXICITIES AND DOSING DELAYS/DOSE MODIFICATIONS

Dose delays and modifications will be made using the following recommendations. Toxicity assessments will be done using the CTEP NCI Common Terminology Criteria for Adverse Events (CTCAE) version 4.0, which is identified and located on the CTEP website at: [http://ctep.cancer.gov/protocolDevelopment/electronic\\_applications/ctc.htm](http://ctep.cancer.gov/protocolDevelopment/electronic_applications/ctc.htm).

If possible, symptoms should be managed symptomatically. In the case of toxicity, appropriate medical treatment should be used (including anti-emetics, anti-diarrheals, etc.).

All adverse events experienced by participants will be collected from the time of the first dose of study treatment, through the study and until the final study visit. Participants continuing to experience toxicity at the off study visit may be contacted for additional assessments until the toxicity has resolved or is deemed irreversible.

### 6.1 Anticipated Toxicities for Brentuximab, Adriamycin, Dacarbazine

#### 6.1.1 Anticipated Toxicities for Brentuximab

A list of the adverse events and potential risks associated with the agents administered in this study appear below. Most toxicities related to brentuximab in the phase I and II studies were Grade 2 or less. A table detailing the Grade 3 toxicities in the phase II studies is below.

Peripheral neuropathy has been commonly reported in the phase II with 44% of patients having peripheral sensory neuropathy, and 9% peripheral motor neuropathy. Of these only 11% were Grade 3 and there were no Grade 4 events. The neuropathy was reversible in nearly all patients with median resolution of 6.6 weeks.

Neutropenia occurred in 21% of patients in the phase II studies with 20% of patients  $\geq$  Grade 3 (13% Grade 3 and 7% Grade 4). Neutropenia  $\geq$  Grade 3 tended to develop after a median of 2 doses and lasted a median of approximately 1 week. Of the 7% of patients with Grade 4 neutropenia, only 3 had neutropenia that lasted  $\geq$  7 days.

Additional toxicity data is as follows:

**Treatment-emergent adverse events  $\geq$  Grade 3 occurring in  $\geq$ 2 HL or systemic ALCL patients in the phase 2 population (Studies SG035-0003 and SG035-0004)**

	HL SG035-0003 (N=102)			ALCL a SG035-0004 (N=58)		
	n (%)			n (%)		
	Grade			Grade		
	$\geq$ 3	4	5	$\geq$ 3	4	5
Any event	56 (55)	14 (14)	1 (1)	35 (60)	9 (16)	6 (10)
Neutropenia	20 (20)	6 (6)	0	12 (21)	5 (9)	0
Thrombocytopenia	8 (8)	2 (2)	0	8 (14)	3 (5)	0
Peripheral sensory neuropathy	8 (8)	0	0	6 (10)	0	0
Anaemia	6 (6)	1 (1)	0	4 (7)	0	0
Hyperglycaemia	4 (4)	0	0	1 (2)	0	0
Fatigue	2 (2)	0	0	2 (3)	1 (2)	0
Abdominal pain	2 (2)	1 (1)	0	1 (2)	0	0
ALCL recurrent	0	0	0	3 (5)	0	3 (5)
Diarrhoea	1 (1)	0	0	2 (3)	0	0
Hypokalaemia	1 (1)	0	0	2 (3)	0	0
Peripheral motor neuropathy	1 (1)	0	0	2 (3)	0	0
Pulmonary embolism	2 (2)	2 (2)	0	1 (2)	0	0
Pyrexia	2 (2)	0	0	1 (2)	0	0
Syncope	2 (2)	0	0	1 (2)	1 (2)	0
Urinary tract infection	1 (1)	0	0	2 (3)	0	0
Anxiety	2 (2)	0	0	0	0	0
Deep vein thrombosis	0	0	0	2 (3)	0	0
Demyelinating polyneuropathy	2 (2)	0	0	0	0	0
Hodgkin's disease recurrent	2 (2)	0	1 (1)	0	0	0
Mycosis fungoides	0	0	0	2 (3)	0	0
Pain in extremity	0	0	0	2 (3)	1 (2)	0
Pneumonitis	2 (2)	1 (1)	0	0	0	0
Pyelonephritis	2 (2)	0	0	0	0	0
Vomiting	0	0	0	2 (3)	0	0
Weight decreased	0	0	0	2 (3)	0	0

Preferred terms are sorted by descending frequency by " $\geq$ 3" in the phase 2 population (Studies SG035-0003 and SG035-0004).

### 6.1.2 Anticipated Toxicities for Adriamycin

Side Effects for Adriamycin include:

1. Hematologic: Leukopenia (dose-limiting), also thrombocytopenia and anemia. Nadir 10-14 days, recovery customarily within 21 days.
2. Dermatologic: Alopecia; hyperpigmentation of nail beds and dermal creases; radiation recall.
3. Gastrointestinal: Nausea and vomiting, sometimes severe; anorexia, diarrhea; mucositis
4. Cardiovascular: Arrhythmias, ECG changes; rarely sudden death. Congestive heart failure due to cardiomyopathy related to total cumulative dose; risk is greater with total doses > 550 mg/m^2, mediastinal irradiation pre-existing cardiac disease, advanced age.
5. Other: Red discoloration of urine; fever; anaphylactoid reaction.
6. Local effects: Vesicant if extravasated; flush along vein, facial flush.

CONFIDENTIAL

This document is confidential. Do not disclose or use except as authorized.

**Nursing/Patient Implications:**

1. Monitor CBC, platelet counts.
2. Vesicant - do not extravasate. Refer to extravasation protocol if inadvertent infiltration occurs.
3. Advise patient of alopecia. Instruct on how to obtain wig, hairpiece, etc. Hair loss generally occurs 2-4 weeks after injection and is usually complete.
4. Advise patient of red discoloration of urine for 24 hours after administration of the drug.
5. Administer antiemetics as indicated.
6. Assess for stomatitis and treat symptomatically. Generally occurs 7-10 days after injection.
7. Be aware of "Adria" flare - most common reaction consists of an erythematous streak up the vein. It is associated with urticaria and pruritus. Occasionally the use of corticosteroids and/or antihistamines has been useful.
8. Monitor for signs and symptoms of cardiomyopathy. Calculate total cumulative dose with each administration.

**6.1.3 Anticipated Toxicities for Dacarbazine**

**Side Effects for Dacarbazine include:**

1. Hematologic: Myelosuppression; nadir of WBC and platelet depression occurs approximately 21-25 days after treatment.
2. Dermatologic: Alopecia; facial flushing; extravasation may result in severe pain but has not resulted in tissue damage. Rapid IV push may result in pain along injection site or thrombophlebitis.
3. Gastrointestinal: Severe nausea and vomiting which characteristically lessens with each subsequent daily dose.
4. Hepatic: Increased AST, ALT.
5. Renal: Increased serum creatinine, BUN.
6. Neurologic: Facial paresthesia.
7. Other: Flu-like syndrome (with fever, malaise, myalgia) rarely occurs about 7 days after treatment and lasts 1-3 weeks. Rarely Anaphylaxis.

**Nursing/Patient Implications:**

1. Administer prophylactic and prn anti-emetics.
2. Monitor CBC, platelet count.
3. May cause pain, burning of the vein with rapid administration. This can be minimized by decreasing the rate of infusion

**6.2 Toxicity Management and Dose Modifications/Delays**

**6.2.1 Supportive care:**

Participants should receive full supportive care per institutional routine including blood products, antibiotics, antiemetics, and bowel regimen at the discretion of the provider.

### 6.2.2 Steroids:

Treatment with steroids for pre-existing conditions, adrenal insufficiency or nausea is allowed provided on a stable dose.

### 6.2.3 Hematologic Toxicity:

Blood counts should be checked on the day of or day before treatment. Hematologic guidelines are extrapolated from the accepted standard of care with ABVD, which is routinely administered at full dose in the setting of neutropenia, in the absence of fever. This is in recognition that though neutropenia is common, the duration of neutropenia is short and fever and infectious complications are uncommon. G-CSF is not routinely included in the care of these patients outside of the setting of febrile neutropenia or infections.

Blood Counts			Administer % of Full Dose
ANC (neutrophils+bands)		PLTs	Brentuximab, Adriamycin, Dacarbazine Dosing
≥500	And	≥50,000	100%
<500 and patient afebrile (temp <100.5 F)	And	≥50,000	100%. G-CSF support may be included at discretion of treating investigator.
<500 and patient febrile (temp ≥100.5 F)	Or	<50,000	Hold all chemotherapy and recheck within one week. Treatment of neutropenic fever per institutional guidelines. Restart at full dose on schedule or within one week after counts have rebounded to ANC ≥500 and PLT ≥75,000. G-CSF should be included for future cycles at treating physician's discretion. Treatment may be held for a maximum of 2 weeks, after which patients will be removed from study.

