We conducted a phase 2 study of 34 patients with non-bulky limited stage classical Hodgkin lymphoma, which completed accrual in 2014. Though data are immature, the treatment appeared highly effective and overall well tolerated. Preliminarily, all patients achieved complete response after 2 cycles of combination brentuximab-AD and no patients required more than 4 cycles of combination chemotherapy. One patient did relapse after achieving remission and was successfully treated with second-line therapy. One additional patient developed neutropenic sepsis and died in remission during therapy. An initially high rate of neutropenic fever was observed, prompting a protocol amendment requiring the use of GCSF support, after which the incidence of infection and neutropenic fever was much lower.

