### 6.2.4 Hepatic Dysfunction

LFT's should be checked on the day of or day prior to treatment. No dose modification required for total bilirubin less than 1.5 mg/dL. Participants with total bilirubin of 1.5 to 2.0 mg/dL at study entry (and not due to Gilbert's disease) will be initiated at a 50% dose reduction of Adriamycin. For total bilirubin greater than 1.5 mg/dL on day 1 or 15, Adriamycin will be administered as below. Brentuximab vedotin will be held for ≥ grade 3 bilirubin (>3 mg/dL) until toxicity is ≤ grade 2. Upon restarting, the brentuximab dose will be reduced to 0.8 mg/kg. If a second dose reduction is required, dose will be reduced to 0.6 mg/kg. There are no dose reductions for dacarbazine based on bilirubin.

Total Bilirubin (mg/dL)	% Brentuximab Dose	% Adriamycin Dose	% Dacarbazine Dose
<1.5	100%	100%	100%
1.5 – 3.0	100%	50%	100%
>3.0-5.0	0%	25%	100%
>5.0	0%	0%	100%

CONFIDENTIAL

This document is confidential. Do not disclose or use except as authorized.

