### 6.2.6 Gastrointestinal toxicity

- Mucositis, dysphagia and diarrhea:

For  $\geq$  Grade 3 gastrointestinal toxicities mentioned above, treatment will be held until toxicity decreases to  $\leq 1$  or baseline, after which treatment will be resumed at full dose. Treatment may be held for a maximum of 2 weeks, after which participants will be removed from study.

- Constipation:

Start stool softeners and mild bowel stimulants (docusate sodium 100 mg po tid plus senna and/or psyllium and/or milk of magnesia and/or Miralax). Increase regimen and add additional agents as needed.

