### 6.2.7 Peripheral nervous system toxicity

PERIPHERAL NERVOUS SYSTEM TOXICITY		
Grade	Brentuximab dose	Comments
Grade 1	1.2 mg/kg (100%)	
Grade 2	Reduce dose to 0.8 mg/kg.	
Grade 3	Withhold dose until toxicity is < Grade 2 or has returned to baseline. Resume at a dose of 0.8 mg/kg. If dose has already been reduced to 0.8 mg/kg, reduce dose to 0.6 mg/kg.	While brentuximab is held, the other agents will continue as described, provided treatment criteria are met. The dose of brentuximab will not be re-escalated.
Grade 4	-----	Patient to come off of study

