### 6.2.9 Other Brentuximab toxicities:

All other Grade 3-4 toxicity considered possibly, probably, or definitely related to brentuximab (Not including hematologic, cardiac, hepatic, gastrointestinal, peripheral nervous system, or alopecia).

Subjects will be removed from study treatment if a second episode of grade 3-4 toxicity occurs despite dose reduction according to table below.

CONFIDENTIAL

This document is confidential. Do not disclose or use except as authorized.

OTHER TOXICITY			
Grade	Brentuximab dose	AD doses	Comments
Grade 1	1.2 mg/kg (100%)	100%	
Grade 2	1.2 mg/kg (100%)	100%	
Grade 3	Withhold dose until toxicity is $\leq$ Grade 2 or has returned to baseline. Reduce the dose to 0.8 mg/kg. If a second dose reduction is required, dose will be reduced to 0.6 mg/kg.	Withhold dose until toxicity is $\leq$ Grade 2 or has returned to baseline, then resume at full dose.	The dose of brentuximab will not be re-escalated.
Grade 4	Withhold dose until toxicity is Grade $\leq 2$ or has returned to baseline, then reduce dose to 0.8 mg/kg and resume treatment, or discontinue at the discretion of the investigator. If a second dose reduction is required, dose will be reduced to 0.6 mg/kg, or discontinue at the discretion of the investigator.	Withhold dose until toxicity is Grade $\leq 2$ or has returned to baseline, then resume at full dose.	The dose of brentuximab will not be re-escalated.

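### In 6.2.3, treatment held for neutropenic fever may restart at full dose on blood counts alone, without the fever having resolved

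*Combined protocol and SAP*

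**What the plan says.** Section 6.2.3 (Hematologic Toxicity) takes its guidance from ABVD, "which is routinely administered at full dose in the setting of neutropenia, in the absence of fever". The table that follows has three rows:

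- **Row 1:** ANC ≥500 and platelets ≥50,000. All three drugs at 100%. No temperature condition.
- **Row 2:** ANC <500, temperature <100.5 F and platelets ≥50,000. All three drugs at 100%, with G-CSF optional.
- **Row 3:** either ANC <500 with temperature ≥100.5 F, or platelets <50,000. All three drugs are held, counts are repeated inside a week, and neutropenic fever is treated under local guidelines.

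The rule for ending a row 3 hold is: "Restart at full dose on schedule or within one week after counts have rebounded to ANC ≥500 and PLT ≥75,000". A hold may last at most 2 weeks, after which the patient leaves the study.

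Section 6 introduces all of its rules in these terms: "Dose delays and modifications will be made using the following recommendations".

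**The concern.** The stated reason for dosing through neutropenia is that the patient has no fever. The table respects this on the way into a hold but not on the way out. A patient stopped because of fever can, on the written words, be given full-dose brentuximab, Adriamycin and dacarbazine again with the fever still present, once the counts have moved past two thresholds.

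What is at stake is the safety of individual patients. G-CSF is discretionary in this trial (5.1 and 6.2.3). Section 2.1 reports that the sponsor's preceding trial saw a high rate of neutropenic fever at first and was amended to require G-CSF. That rate may not carry over: 2.2 links it to brentuximab added to AVD, and 2.3 expects less neutropenia without vinblastine. That expectation is still a hypothesis, so the wording of a dosing rule should not lean on it.

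**Working it through.** The plan gives no figure to reproduce here. The check applies the three rows and the restart rule of 6.2.3 exactly as written to chosen values of ANC, platelets (PLT) and temperature.

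**Step 1. What decides a hold below ANC 500?** Fix PLT ≥50,000 and ANC <500. Rows 2 and 3 then differ only in temperature.

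| ANC | PLT | Temp (F) | Table result |
|---|---|---|---|
| 499 | 60,000 | 100.4 | Row 2: 100% |
| 499 | 60,000 | 100.5 | Row 3: hold |

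With adequate platelets, an ANC below 500 never causes a hold by itself. Fever decides.

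**Step 2. What ends the hold?** The restart rule asks for ANC ≥500 and PLT ≥75,000.

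| ANC | PLT | Temp (F) | Restart criterion |
|---|---|---|---|
| 600 | 80,000 | 98.6 | met |
| 600 | 80,000 | 103 | met |
| 499 | 80,000 | 98.6 | not met |

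Temperature makes no difference to the result. The third line shows the reverse side: a held patient whose fever has gone must wait at ANC 499, although row 2 would give full dose at those same values to a patient who had not been held.

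**Step 3. Does row 1 behave the same way without a prior hold?**

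| ANC | PLT | Temp (F) | Table result |
|---|---|---|---|
| 499 | 60,000 | 103 | Row 3: hold |
| 500 | 60,000 | 103 | Row 1: 100% |
| 600 | 60,000 | 103 | Row 1: 100% |
| 600 | 40,000 | 103 | Row 3: hold, because of platelets |

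Yes, provided platelets are at least 50,000.

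**Step 4. Does another section supply the missing condition?**

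- 5.1 sends the reader back to section 6 for dosing in neutropenia.
- 3.2.6 excludes active infection, but only at entry.
- 5.2 lists reasons to end therapy, including intercurrent illness. It contains no rule for holding or restarting on a dosing day because of fever.
- 6.2.9 covers "All other Grade 3-4 toxicity considered possibly, probably, or definitely related to brentuximab" and leaves out hematologic toxicity. It could hold treatment for a related grade 3-4 infection, but it does not address fever.

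No written rule makes the end of the fever a condition for restart, and none holds treatment for fever itself at ANC ≥500.

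**The case against.** The strongest reply is that the row 3 trigger is a conjunction: ANC <500 and fever together, or low platelets. Temperature alone is never a trigger. Once ANC reaches 500 the conjunction is false, so restart does follow recovery from the written trigger, and for platelets the rule is stricter than the hold (75,000 against 50,000). This is correct, and it limits the point. A reader might set 6.2.3 beside the other hold rules, such as "Brentuximab vedotin will be held for ≥ grade 3 bilirubin (>3 mg/dL) until toxicity is ≤ grade 2" in 6.2.4, "treatment will be held until toxicity decreases to" a low grade or baseline in 6.2.6, or "Withhold dose until toxicity is < Grade 2 or has returned to baseline" in 6.2.7, and conclude that 6.2.3 alone drops its trigger at restart. The documents do not support that count, because half of an AND condition is not a separate trigger. What the reply leaves standing is Step 1: with adequate platelets, fever is the deciding half, and it is the half that the restart rule omits.

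Second, the table concerns blood counts and is not a complete dosing order. A patient with grade 3 mucositis and good counts also falls in row 1 and is still held under 6.2.6. That is fair, but for mucositis a rule exists elsewhere; for fever at ANC ≥500 none does.

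Third, safeguards exist: the premise sentence in 6.2.3 itself, local fever guidelines, the one-week restart window, the ±3 day treatment window in section 5, discussion of delays with the principal investigator (4.1 and 4.3), and the status of section 6 as recommendations. These make dosing of such a patient unlikely, and this stands. None of them is written as a condition for restart.

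Fourth, section 2.1 says of the preceding trial: "One additional patient developed neutropenic sepsis and died in remission during therapy". A reader might infer that this death shows the harm done by such a gap. It does not. Nothing there says that anyone was dosed or restarted while febrile, and the remedy reported was G-CSF.

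**Conclusion.** The point holds as a gap between the stated premise of 6.2.3 and its restart rule, with the same gap in row 1 just above ANC 500. It rests on a literal reading of the table and on platelets being at or above the relevant threshold (75,000 for restart, 50,000 for row 1).

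Its size is small: a minor safety wording change and a cheap improvement. The documents do not say how often fever would coincide with ANC ≥500 on a dosing day, so no number of patients and no harm estimate can be given. Multiplying patients by doses would only count uses of the table. The sample size, power and type I error in 13.1.1 are not affected.

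A reader might also call this a formal contradiction within 6.2.3. That goes too far: the section gives no ANC definition of neutropenia, so full dosing of a febrile patient at ANC 600 departs from the spirit of the premise without strictly contradicting it.

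**What to change.** In the hold row of the 6.2.3 table, after a hold for neutropenic fever, allow restart only when all of the following are met:

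- ANC ≥500;
- platelets ≥75,000;
- temperature <100.5 F, or the remaining fever judged by the investigator not due to infection.

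The last alternative matters because stages IB and IIB are eligible (3.1.1), and a patient with tumour fever and recovered counts should not be held until the 2-week limit. A hold for platelets alone keeps its present restart rule.

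Optionally, the sponsor may add the same afebrile condition to row 1 below an ANC cut-off of its choice. The documents do not settle that cut-off, and clinicians could differ on it.

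The cost is one clause in one table cell by amendment, or two cells with the option. No new tests are needed, because 8.2 already requires vital signs and a blood count on each treatment day. The downside is a few short holds that count toward the 2-week limit and slightly reduce dose intensity, which 5.1 warns may worsen outcome.

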### 6.2.4 Hepatic Dysfunction

LFT's should be checked on the day of or day prior to treatment. No dose modification required for total bilirubin less than 1.5 mg/dL. Participants with total bilirubin of 1.5 to 2.0 mg/dL at study entry (and not due to Gilbert's disease) will be initiated at a 50% dose reduction of Adriamycin. For total bilirubin greater than 1.5 mg/dL on day 1 or 15, Adriamycin will be administered as below. Brentuximab vedotin will be held for ≥ grade 3 bilirubin (>3 mg/dL) until toxicity is ≤ grade 2. Upon restarting, the brentuximab dose will be reduced to 0.8 mg/kg. If a second dose reduction is required, dose will be reduced to 0.6 mg/kg. There are no dose reductions for dacarbazine based on bilirubin.

Total Bilirubin (mg/dL)	% Brentuximab Dose	% Adriamycin Dose	% Dacarbazine Dose
<1.5	100%	100%	100%
1.5 – 3.0	100%	50%	100%
>3.0-5.0	0%	25%	100%
>5.0	0%	0%	100%

CONFIDENTIAL

This document is confidential. Do not disclose or use except as authorized.

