## **1. OBJECTIVES**

### **1.1 Study Design**

This is an open label single arm phase II study to assess the efficacy and safety of Brentuximab Vedotin (hereafter referred to as brentuximab) in combination with Adriamycin and Dacarbazine (AD) in patients with previously untreated stage I and II non-bulky classical Hodgkin lymphoma (cHL). All patients will receive combination therapy with brentuximab and AD with all agents administered on days 1 and 15 of each 28 day cycle. Brentuximab will be administered at 1.2 mg/kg. AD will be administered at standard doses (Adriamycin 25mg/m^2, Dacarbazine 375 mg/m^2). Interim restaging PET-CT will be performed following cycle 2. Patients with progressive disease will be taken off study. Patients in CR will receive a total of 4 cycles of therapy; patients with stable disease or partial response will receive a total of 6 cycles. There is no planned radiotherapy for patients achieving a complete remission at the end of therapy.

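### Section 6.2.4 does not reconcile its text and its table for a patient restarting brentuximab after a bilirubin hold: 0.8 mg/kg in the text, 100% in the table

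*Combined protocol and SAP*

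**What the plan says.** The full brentuximab dose is set in section 1.1: "Brentuximab will be administered at 1.2 mg/kg".

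Section 6.2.4 gives brentuximab its own rule for raised bilirubin. The hold and release are: "Brentuximab vedotin will be held for ≥ grade 3 bilirubin (>3 mg/dL) until toxicity is ≤ grade 2". The restart dose follows: "Upon restarting, the brentuximab dose will be reduced to 0.8 mg/kg". Then comes the next step down: "If a second dose reduction is required, dose will be reduced to 0.6 mg/kg".

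The same paragraph says, without an exception for a patient who was previously held: "No dose modification required for total bilirubin less than 1.5 mg/dL". It introduces the table by reference to one drug only: "For total bilirubin greater than 1.5 mg/dL on day 1 or 15, Adriamycin will be administered as below".

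The table nevertheless has a brentuximab column. It reads 100% at <1.5 mg/dL, 100% at 1.5–3.0 mg/dL, and 0% in the two rows above 3.0 mg/dL. It shows neither 0.8 nor 0.6 mg/kg.

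Sections 6.2.7 (neuropathy) and 6.2.9 (other brentuximab toxicities) both say that a reduced brentuximab dose is not raised again. Section 6.2.4 says nothing on this, and 6.2.9 excludes hepatic toxicity from its scope.

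**The concern.** The paragraph sets the dose by the patient's history (was brentuximab held?), whereas the table sets it by that day's bilirubin. Nothing connects the two. Someone who goes straight to the table for a patient whose bilirubin has fallen to 3.0 mg/dL or below finds 100%, with no sign that a reduction applies.

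Two things are at stake. One is patient safety. The label included with the protocol reports serious hepatotoxicity, including cases after rechallenge (label section 5.8), and MMAE exposure about 2.2 times higher in hepatic impairment (label section 8.7). The other is uniform delivery of the regimen. The protocol provides for sites outside the lead consortium (sections 4.3 and 12.4), and the nursing page sends staff to section 6.2 for dose modifications. Sites may therefore resolve the same case differently.

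**Working it through.** The plan gives no figure for this point to reproduce, so the check is a side-by-side reading plus dose ratios.

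**1. Which table rows can apply at restart?** The protocol equates grade 3 or higher with more than 3 mg/dL and releases the hold at grade 2 or lower. By its own parenthesis, restart is possible at 3.0 mg/dL or below. That leaves two rows:

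| Bilirubin (mg/dL) | Text, after a hold | Table |
|---|---|---|
| <1.5 | 0.8 mg/kg | 100% |
| 1.5–3.0 | 0.8 mg/kg | 100% |

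**2. 100% of what?** The table does not say. Three features of section 6.2 point to the full dose:
- The table in 6.2.3, which covers brentuximab as well, is expressed as a percentage of full dose.
- The tables in 6.2.7 and 6.2.9 print 1.2 mg/kg beside 100%.
- The Adriamycin column of the 6.2.4 table works only on a full-dose base. A patient entering at 1.5–2.0 mg/dL (not due to Gilbert's disease) starts at a 50% Adriamycin reduction, and the 1.5–3.0 row says 50%. On a current-dose base that patient would drop to 0.50 × 0.50 = 25% with bilirubin unchanged.

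**3. Size of the gap under each reading.**
- Full-dose base: table 1.2 mg/kg, text 0.8 mg/kg. 0.8/1.2 = 66.7%, and 1.2/0.8 = 1.50, so the table dose is 50% higher.
- Current-dose base: 100% of 0.8 mg/kg is 0.8 mg/kg, and there is no conflict.

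In milligrams on the full-dose base, at assumed weights:
- 45 kg: 54 versus 36 mg
- 70 kg: 84 versus 56 mg
- 100 kg (the dosing cap): 120 versus 80 mg

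**4. Later visits.** Suppose the patient restarts at 0.8 mg/kg and bilirubin is below 1.5 mg/dL at the next day 1 or 15. The table again shows 100%, and the sentence on values below 1.5 mg/dL has no exception for an earlier hold. The statements in 6.2.7 and 6.2.9 cannot be borrowed, since one concerns neuropathy and the other excludes hepatic toxicity.

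**5. How many patients?** The documents give no expected number. A rough indication comes from the section 6.1.1 table of grade 3 or higher events seen in at least 2 patients in either single-agent phase II study (102 + 58 = 160 patients). It lists no bilirubin event. Assuming at most one such event per study, the rate is at most 2/160 = 1.25%, or 0.0125 × 34 ≈ 0.4 patients here. This is an indication, not a bound: those patients received brentuximab alone at 1.8 mg/kg every 3 weeks, and bilirubin changes could be recorded under other terms.

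**6. Primary endpoint.** Promising at 31 or more complete responses in 34, with rates of 81% and 95%, gives a type I error of 0.0906 and power of 0.912. These agree with the 0.09 and 91% in section 13.1.1 and do not depend on the bilirubin rule.

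**The case against.** The strongest reply is that the section, read as a whole, yields one instruction. The restart sentence addresses exactly this patient. The lead-in sends the reader to the table for Adriamycin only. The 0% rows agree with the hold, and the table has no row for a restart, so it may simply not address that case. The step to 0.6 mg/kg presupposes a patient still at 0.8 mg/kg, which implies that the reduction persists. In 6.2.7 and 6.2.9, too, the 100% entry is a default for an unreduced patient and does not cancel an earlier reduction.

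Most of this stands. A reader might infer that the protocol orders two doses for every patient who restarts. The documents do not support that: a careful reader of the whole section would probably give 0.8 mg/kg, and the conflict arises only where someone doses from the table without the paragraph. A reader might also infer a twofold gap after a second reduction (1.2 against 0.6 mg/kg). That does not stand as the size of the problem either, because the second step itself implies that the first reduction was kept.

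The reply does not remove the gap. The table's brentuximab column contains operative 0% entries, so it is not there for Adriamycin alone. The current-dose reading of 100% has less support than the full-dose reading. And 6.2.7 and 6.2.9 found it necessary to state the bar on re-escalation, whereas 6.2.4 leaves it to inference.

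**Conclusion.** The point holds as an unreconciled paragraph and table in a dose-modification rule. The restart sentence probably governs. However, the table carries no link to it, the base of the percentage is unstated, and re-escalation is not addressed in 6.2.4. If 100% means full dose, as in the other percentage-based brentuximab tables of section 6.2, a site using the table alone could give 1.2 instead of 0.8 mg/kg, 50% more, at restart or later. If 100% means the current dose, the two agree.

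The number of patients exposed to this is unknown and likely small. Besides the indication from the single-agent studies, entry requires bilirubin of at most 2 unless due to Gilbert's disease (section 3.1.6). Section 5.2 also ends treatment for toxicity delays beyond 2 weeks and for grade 4 events felt to be related to brentuximab. The primary-endpoint operating characteristics are unaffected. The case for acting rests on patient safety and consistency across sites, and the correction is cheap. No view is taken on which dose is right.

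**What to change.** Reconcile the paragraph and the table in section 6.2.4 with three additions:
- State the base of the percentages in the brentuximab column (full dose or the patient's current dose).
- Add a footnote linking that column to the restart rule for patients with a prior hold.
- State in 6.2.4 whether brentuximab may be re-escalated after a bilirubin-related reduction.

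Which dose applies, and whether re-escalation is permitted, is for the sponsor to decide. The cost is a footnote and a sentence or two in an amendment. Sample size, data collection and analysis do not change.
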